### **15.4. Interim Analysis**

There are no planned interim analyses. However, safety and erythroid response data will be reviewed periodically throughout the study.

### **15.5. Deviation from Original Analysis Plan**

A formal Statistical Analysis Plan (SAP) for the analysis and presentation of data from this study will be prepared before the database lock. Deviations from the statistical analyses outlined in this protocol will be indicated in this plan; any further modifications will be noted in the final clinical study report.

## **16. SOURCE DOCUMENTATION AND INVESTIGATOR FILES**

### **16.1. Study Monitoring**

The clinical monitor will arrange to visit the clinical sites at regular intervals during the study. The monitoring visits must be conducted according to the applicable ICH and GCP guidelines to ensure protocol adherence, quality of data, drug accountability, compliance with regulatory requirements, and continued adequacy of the clinical sites and their facilities. During these visits, CRFs and other data related to the study will be reviewed and any discrepancies or omissions will be resolved. The clinical monitor will be given access to study-relevant source documents (including medical records) for purposes of source data verification.

### **16.2. Audits and Inspections**

The investigators and clinical sites will permit trial-related monitoring, audits, IEC review, and regulatory inspections as requested by FDA or other health authorities and the sponsor or designee. In addition to CRFs, the clinical site will permit direct access to source data/documents (i.e., original medical records, laboratory reports, hospital documents, progress reports, signed ICFs, etc.). During and/or after completion of the study, quality assurance officers named by the sponsor or the regulatory authorities may wish to perform on-site audits. The investigator is expected to cooperate with any audit and provide assistance and documentation (including source data) as requested.

## **17. QUALITY CONTROL AND QUALITY ASSURANCE**

### **17.1. Data Quality Control and Quality Assurance**

#### **17.1.1. Investigator Responsibility**

The investigator is responsible for ensuring the study is conducted according to the protocol, Code of Federal Regulations, GCP, and applicable regulatory requirements. The investigator's responsibilities are outlined in these documents and must include the responsibility to obtain a signed informed consent prior to patient participation in the study.

#### **17.1.2. Protocol Modifications**

The investigator should not modify the protocol without agreement from the sponsor and prior review or approval by the IEC, unless an emergency situation requires protocol modification to ensure the safety of patients. Any deviations from the protocol should be documented by the investigator or designee.

## **18. CONFIDENTIALITY**

To maintain patient privacy, all CRFs, study drug accountability records, study reports and communications will identify the patient by the assigned patient identification number. The investigator will grant clinical monitor(s) and auditor(s) from the sponsor or designee and regulatory authorities' access to the patient's original medical records for verification of data gathered on the CRFs and to audit the data collection process. The patient's confidentiality will be maintained and will not be made publicly available. The patient's medical information will only be released to the extent permitted by the applicable laws and regulations.

All information regarding the investigational product supplied by the sponsor to the investigator is privileged and confidential information. The investigator agrees to use this information to accomplish the study and will not use it for other purposes without consent from the sponsor. It is understood that there is an obligation to provide the sponsor with complete data obtained during the study. The information obtained from the clinical study will be used towards the development of the investigational product and may be disclosed to regulatory authorities, other investigators, corporate partners, or consultants as required.

## **19. PUBLICATION POLICY**

All information concerning ACE-536 is considered confidential and shall remain the sole property of the sponsor. The investigator(s) agree to use this information only in conducting the study and shall not use it for any other purposes without the sponsor's written approval. The investigator(s) agree not to disclose the sponsor's confidential information to anyone except to persons involved in the study that need such information to assist in conducting the study, and then only on like terms of confidentiality and non-use.

It is understood by the investigator(s) that the information developed from this clinical study will be used by the sponsor in connection with the development of ACE-536, and therefore may be disclosed as required to regulatory agencies. To allow for the use of the information derived from clinical studies, it is understood that there is an obligation to provide the sponsor with complete test results and all data developed in the study.

No publication or disclosure of study results will be permitted except as specified in a separate, written, agreement between the sponsor and the investigator(s).

## **20. PROTOCOL AMENDMENTS**

Protocol amendments that impact patient safety, change the scope of the investigation, or affect the scientific quality of the study must be approved by the IEC and submitted to the appropriate regulatory authorities before implementation.

In the event that the protocol needs to be modified immediately to eliminate an apparent hazard to a patient, the sponsor will implement the protocol change and subsequently amend the protocol and notify the regulatory authorities and/or the IEC, as appropriate.

## **21. DATA HANDLING AND RECORDKEEPING**

### **21.1. Case Report Form Completion**

CRFs will be completed for each enrolled patient. It is the investigator's responsibility to ensure the accuracy, completeness, and timeliness of the data reported in the patient's CRF. Source documentation supporting the CRF data should indicate the patient's participation in the study and should document the dates and details of study procedures, AEs, and patient status.

Investigators will maintain copies of the CRFs at the clinical site. For patients who discontinue or terminate from the study, the CRFs will be completed as much as possible, and the reason for the discontinuation or termination clearly and concisely specified on the appropriate CRF.

### **21.2. Retention of Records**

The investigator will maintain all study records according to ICH-GCP and applicable regulatory requirements. Records will be retained for at least 2 years after the last marketing application approval or 2 years after formal discontinuation of the clinical development of the investigational product, or according to applicable regulatory requirements. If the investigator withdraws from the responsibility of keeping the study records, custody must be transferred to a person willing to accept the responsibility. The sponsor must be notified in writing if a custodial change occurs.

## **22. STUDY FINANCE AND INSURANCE**

### **22.1. Study Finance**

The costs necessary to perform the study will be agreed with each Investigator and will be documented in a separate financial agreement that will be signed by the Investigator and Acceleron Pharma Inc. or designee, prior to the study commencing.

Participants may be reimbursed for study-related travel.

### **22.2. Insurance**

The Sponsor has insurance coverage for study related ACE-536 induced injury and other liabilities incurred during clinical studies which will provide compensation for any study related injury according to the guidelines set out by the Association of the British Pharmaceutical Industry (ABPI), namely "Clinical Studies Compensation for Medicine Induced Injury.

## 24. APPENDICES

### 24.1. Appendix 1: WHO Classification and Criteria for the Myelodysplastic Syndromes

Disease	Blood findings	Bone marrow findings
Refractory cytopenia with unilineage dysplasia (RCUD): (refractory anemia [RA]; refractory neutropenia [RN]; refractory thrombocytopenia [RT])	Unicytopenia or bicytopenia a  No or rare blasts (< 1%) b	Unilineage dysplasia: ≥ 10% of the cells in one myeloid lineage  < 5% blasts  < 15% of erythroid precursors are ring sideroblasts
Refractory anemia with ring sideroblasts (RARS)	Anemia  No blasts	≥ 15% of erythroid precursors are ring sideroblasts  Erythroid dysplasia only  < 5% blasts
Refractory cytopenia with multilineage dysplasia (RCMD)	Cytopenia(s)  No or rare blasts (< 1%) b  No Auer rods  < 1 x10  /L monocytes	Dysplasia in ≥ 10% of the cells in ≥ 2 myeloid lineages (neutrophil and/or erythroid precursors and/or megakaryocytes)  < 5% blasts in marrow  No Auer rods  ± 15% ring sideroblasts
Refractory anemia with excess blasts-1 (RAEB-1)	Cytopenia(s)  < 5% blasts b  No Auer rods  < 1 x10  /L monocytes	Unilineage or multilineage dysplasia  5%-9% blasts b  No Auer rods
Refractory anemia with excess blasts-2 (RAEB-2)	Cytopenia(s)  5%-19% blasts c  Auer rods ± c  < 1 x10  /L monocytes	Unilineage or multilineage dysplasia  10%-19% blasts c  Auer rods ± c

Disease	Blood findings	Bone marrow findings
Myelodysplastic syndrome-unclassified (MDS-U)	Cytopenias  $< 1\%$ blasts b	Unequivocal dysplasia in $< 10\%$ of cells in one or more myeloid lineages when accompanied by a cytogenetic abnormality considered as presumptive evidence for a diagnosis of MDS  $< 5\%$ blasts
MDS associated with isolated del(5q)	Anemia  Usually normal or increased platelet count  No or rare blasts ( $< 1\%$ )	Normal to increased megakaryocytes with hypolobated nuclei  $< 5\%$ blasts  Isolated del(5q) cytogenetic abnormality  No Auer rods

a Bicytopenia may occasionally be observed. Cases with pancytopenia should be classified as MDS-U.

b If the marrow myeloblast percentage is  $< 5\%$  but there are 2% to 4% myeloblasts in the blood, the diagnostic classification is RAEB-1. Cases of RCUD and RCMD with 1% myeloblasts in the blood should be classified as MDS-U.

c Cases with Auer rods and  $< 5\%$  myeloblasts in the blood and less than 10% in the marrow should be classified as RAEB-2. Although the finding of 5% to 19% blasts in the blood is, in itself, diagnostic of RAEB-2, cases of RAEB-2 may have  $< 5\%$  blasts in the blood if they have Auer rods or 10% to 19% blasts in the marrow or both. Similarly, cases of RAEB-2 may have  $< 10\%$  blasts in the marrow but may be diagnosed by the other 2 findings, Auer rod+ and/or 5% to 19% blasts in the blood.

## 24.2. Appendix 2: International Prognostic Scoring System (IPSS) for Myelodysplastic Syndromes (MDS)

Prognostic Variable	IPSS Scoring Value				
	0	0.5	1.0	1.5	2.0
Bone Marrow Blasts (%)	< 5	5-10	—	11-20	21-30
Karyotype a	Good	Intermediate	Poor		
Cytopenias b	0-1	2-3			

a Good = normal, -Y, del(5q), del(20q); Intermediate = other abnormalities;

Poor = complex ( $\geq 3$  abnormalities) or chromosome 7 anomalies

b Neutrophils < 1800/ $\mu$ L, hemoglobin < 10 g/dL, platelets < 100,000/ $\mu$ L.

	IPSS Classification			
Risk Group	Low	Int-1	Int-2	High
Score	0	0.5 - 1.0	1.5 - 2.0	$\geq 2.5$

### 24.3. Appendix 3: ECOG Performance Status

The ECOG scale is used to assess a patient's quality of life in an evaluation by a health professional of the daily activities and how the activities are affected by the disease of the patient.

Grade	ECOG
0	Fully active, able to carry on all pre-disease performance without restriction
1	Restricted in physically strenuous activity but ambulatory and able to carry out work of a light or sedentary nature, e.g., light house work, office work
2	Ambulatory and capable of all self-care but unable to carry out any work activities. Up and about more than 50% of waking hours
3	Capable of only limited self-care, confined to bed or chair more than 50% of waking hours
4	Completely disabled. Cannot carry on any self-care. Totally confined to bed or chair
5	Dead

## 24.4. Appendix 4: International Working Group (IWG) Criteria - Erythroid Response Evaluation

Hematologic Improvement (HI) a	Response Criteria (Responses must last at least 8 weeks)
Erythroid response (Hi-E) (pretreatment Hgb < 11 g/dL)	Hgb increase of $\geq 1.5$ g/dL for patients not transfused; or, as defined by having received less than 4 units of RBCs within 8 weeks of Cycle 1 Day 1 Reduction by $\geq 4$ units of RBCs transfused (for a Hgb $\leq 9.0$ g/dL) during any 8-week period on study, compared with the 8-week period prior to study day 1
Platelet response (HI-P) (pretreatment, $< 100 \times 10^9/L$ )	Absolute increase of $\geq 30 \times 10^9/L$ for patients starting with $> 20 \times 10^9/L$ platelets Increase from $< 20 \times 10^9/L$ to $> 20 \times 10^9/L$ and by at least 100%
Neutrophil response (HI-N) (pretreatment, $< 1.0 \times 10^9/L$ )	At least 100% increase and an absolute increase $> 0.5 \times 10^9/L$

a Pre-treatment counts are averages of at least 2 measurements (not influenced by transfusions)  $\geq 1$  week apart within 28 days prior to Day 1.

Hgb indicates hemoglobin; RBC: red blood cell; HI: hematologic improvement.

**24.5. Appendix 5: National Cancer Institute (NCI) Common Terminology Criteria for Adverse Events (CTCAE) Version 4.0**

See <http://evs.nci.nih.gov/ftp1/CTCAE/CTCAE>

1. INTRODUCTION

This statistical analysis plan (SAP) describes the statistical methods to be used for the analysis of Acceleron protocol A536-03. This SAP should be read in conjunction with the study protocol and electronic case report form (eCRF). This version of the plan has been developed using the protocol amendment 06 dated 05 July 2017.

The SAP will be signed off before the study database lock. Any deviations from the SAP will be described and justified in the final clinical study report (CSR).

2. STUDY OBJECTIVES

Primary Objective:

- To evaluate the proportion of patients who have a modified erythroid response (mHI-E), defined as a hemoglobin increase of ≥ 1.5 g/dL from baseline for ≥ 14 days (in the absence of red blood cell [RBC] transfusions) in low transfusion burden patients, or, a reduction of either ≥ 4 units or $\geq 50\%$ of units of RBCs transfused compared to pre-treatment in high transfusion burden patients.

Secondary Objectives:

- To evaluate safety and tolerability of luspatercept (ACE-536)
- To examine rates of erythroid, neutrophil and platelet (HI-E, HI-N and HI-P) responses (International Working Group [IWG] 2006 criteria¹. See Appendix 3)
- To evaluate time to HI-E response and duration of HI-E response
- To evaluate frequency of RBC transfusions in high transfusion burden patients
- To examine the pharmacokinetic (PK) profile of luspatercept
- To examine other pharmacodynamic (PD) effects (e.g., iron metabolism, erythropoietin, reticulocytes, and bone biomarkers)

Exploratory Objectives:

- To evaluate biomarkers related to the TGF- β superfamily
- Evaluation of self-reported quality of life in the expansion cohort using tools including but not limited to the Functional Assessment of Cancer Therapy-Anemia Scale (FACT-An) questionnaire

3. OVERALL STUDY DESIGN

This is a phase 2, open-label, ascending dose study to evaluate the effects of luspatercept (ACE-536) on anemia in patients with low or intermediate-1 risk MDS who are not currently receiving treatment with an erythropoiesis-stimulating agent (ESA).

3.1. Study Design

Patients who meet the study eligibility criteria will be enrolled within 28 days of screening. Patients in all cohorts will receive luspatercept, administered subcutaneously (SC), every 3 weeks for up to 5 cycles. Dose delay(s) and dose reduction(s) may be required for individual patients as outlined in protocol Section 10.8.1, Patient Dose Modification Rules.

Each dose escalation cohort will consist of a minimum of 3 patients. The dose level of luspatercept for the first cohort will be 0.125 mg/kg and the dose level(s) for subsequent cohort(s) will follow a modified Fibonacci dose escalation scheme with a maximum dose level of 0.25 mg/kg for cohort 2, 0.50 mg/kg for cohort 3, 0.75 mg/kg for cohort 4, 1.0 mg/kg for cohort 5, 1.33 mg/kg for cohort 6, 1.75 mg/kg for cohort 7, and a maximum dose level not to exceed 1.75 mg/kg. Once a minimum of 3 patients in a cohort have completed Study Day 29, the Safety Review Team (SRT) will review preliminary safety and hematologic response data and make recommendations to the Sponsor regarding whether or not to enroll an additional 3 patients in that cohort, enroll a new cohort at a higher or lower dose, or proceed to the expansion cohort.

Expansion cohort 1 (n= approximately 30) will be treated with ACE-536 at a starting dose level of 1.0 mg/kg. Expansion cohort 1 will consist of a minimum of 10 patients who are high transfusion burden (HTB) patients and 10 patients who are low transfusion burden (LTB) patients, if feasible.

Expansion cohort 2 will be treated with ACE-536 at a starting dose level of 1.0 mg/kg. Expansion cohort 2 will be divided into two groups designated expansion cohort 2A and 2B. The targeted accrual for each group will be 25 eligible and evaluable patients but permitted to range from 22 to 28 for administrative reasons. The maximum number of patients treated will be 56.

- Expansion cohort 2A: LTB patients with $\geq 15\%$ ring sideroblasts in the bone marrow (RS+), less than 4 weeks of exposure to erythropoietin stimulating agents (ESAs), and serum erythropoietin (EPO) level ≤ 200 U/L at screening.
- Expansion cohort 2B: Patients with $< 15\%$ ring sideroblasts in the bone marrow (RS-) and ≤ 6 RBC units in 8 weeks prior to cycle 1 day 1 (C1D1). This group will consist of a minimum of 10 patients who have less than 4 weeks of exposure to ESAs and 5 patients who have received ≥ 4 weeks of treatment with ESAs.

Expansion cohort 3 will be treated with ACE-536 at a starting dose level of 1.0 mg/kg. Expansion cohort 3 will consist of patients who are: RS-, have baseline EPO levels of ≤ 500 U/L at screening, are transfused with ≤ 6 RBC units in 8 weeks prior to C1D1, and have no prior ESA treatment. It was planned in the protocol to treat approximately 25 patients in this cohort. At the end of the study, 9 patients were treated.

In the expansion cohorts, a patient's dose level may be titrated based on criteria listed in the protocol Section 10.8.2, Expansion Cohorts Patient Dose Titration. The maximum dose level given to a patient will not exceed the maximum dose level evaluated in the dose escalation

cohorts. Patients in the expansion cohorts will be treated with up to 5 doses of luspatercept administered once every 3 weeks.

Table 1: Dose Escalation

Cohort ^a	Maximum ACE-536 Dose Level ^b (mg/kg)	Number of Patients
1	0.125	3-6
2	0.25	3-6
3	0.50	3-6
4	0.75	3-6
5	1.0	3-6
6	1.33	3-6
7	1.75	3-6
Expansion 1	1.0	30
Expansion 2	1.0	up to 56
Expansion 3	1.0	25 ^c
Planned Total:		up to 153

^a Cohort escalation is based on SRT review and recommendation to enroll additional cohorts and/or the expansion cohort.

^b The ACE-536 dose level for cohort 1 is 0.125 mg/kg. The dose level indicated for all subsequent cohorts is the maximum dose level that can be recommended by the SRT for escalation per the modified Fibonacci dose escalation scheme. Dose escalation will not exceed 1.75 mg/kg.

^c There were 9 patients treated in Expansion 3 by the end of the study.

The total duration of participation for a patient is approximately 28 weeks (4 week screening period, 12 weeks of treatment period and 12 weeks of follow-up period). If a patient has a positive anti-drug antibody (ADA) result at the last visit, the patient may be asked to return for additional ADA testing every three months, until a negative result is obtained or the result is considered to be stabilized.

3.2. Treatment Discontinuation

Patients will be informed that they have the right to discontinue treatment and/or withdraw from the study at any time for any reason without prejudice to their medical care.

A patient may be discontinued from treatment for any of the following reasons:

- Patient's request
- Patient's unwillingness or inability to comply with the protocol
- Pregnancy
- Use of prohibited medication (e.g., ESA)
- Medical reason or adverse event, at the discretion of the investigator and/or the medical monitor
- Lack of effect (e.g., worsening anemia for NTD patients as evidenced by sustained reduction in Hgb by ≥ 2 g/dL over 8 weeks or transfusion dependence), to be discussed with the medical monitor
- Disease progression (as per IWG criteria¹ for altering natural history of MDS. See [Appendix 3](#)):

- For patients with 5-10% blasts, a second bone marrow sample should be collected within 4 weeks for clinical assessment (e.g., cytomorphology, cytogenetics) to confirm progression before discontinuing patients from treatment.
- Persistent increase in white blood cell (WBC) count as per Patient Dose Modifications (protocol Section 10.8)
- Presence of $\geq 1\%$ blasts in peripheral blood as per Patient Dose Modifications in protocol Section 10.8
- Hypersensitivity reaction to study drug
- At the discretion of the sponsor (e.g., termination of the study or a dose level)
-

A patient may be withdrawn from the study for any of the following reasons:

- Patient's request
- Patient's unwillingness or inability to comply with the protocol
- Death
- Lost to follow-up
- At the discretion of the sponsor (e.g., termination of the study)

The reasons for study withdrawal and/or treatment discontinuation must be recorded in the patient's CRF. The investigator must notify the sponsor, the medical monitor and the contract research organization (CRO) immediately when a patient has been discontinued/withdrawn due to an AE. Patients who discontinue treatment early should complete the end of treatment (EOT) follow-up visit at the time of discontinuation and then complete the post-treatment follow-up (PTFU) and end of study (EOS) follow-up visits approximately 28 and 56 days later, respectively.

3.3. Sample Size

There is no formal sample size calculation for the dose escalation portion of the study. A standard dose escalation design will be implemented, and up to 42 patients will be enrolled at up to 7 different dose levels to further evaluate erythroid response.

A sample size of 30 evaluable patients in the expansion cohort will provide approximately 90% power with 1-sided significance level of 0.05 to differentiate an erythroid response rate of 30% from a minimal erythroid response rate of 10% based on Fisher exact test.

A sample size of 25 evaluable patients in each group of expansion cohorts 2 and 3 will provide approximately 80% power with 1-sided significance level of 0.05 to differentiate an erythroid response rate of 30% from a minimal erythroid response rate of 10 % based on Fisher exact test.

4. ANALYSIS POPULATIONS

For all analysis populations, patients will be analyzed according to assigned cohort.

4.1. Intent-to-Treat (ITT) Population

The intent-to-treat (ITT) population will consist of all patients who have received at least 1 dose of ACE-536. This population will be used for all efficacy analyses.

4.2. Safety Population

Safety population will consist of all patients who received at least 1 dose of ACE-536. This population will be used for all safety analysis.

4.3. Pharmacokinetics (PK) Population

Pharmacokinetics population will include all patients who have received at least 1 dose of ACE-536 and have sufficient pharmacokinetic samples collected and assayed for PK analysis.

5. STATISTICAL METHODOLOGY

5.1. Definitions

Low Transfusion Burden (LTB)

LTB patients are defined as those who received < 4 units of RBCs within 8 weeks prior to Cycle 1 Day 1.

High Transfusion Burden (HTB)

HTB patients are defined as those who required ≥ 4 units of RBCs within 8 weeks prior to Cycle 1 Day 1.

Baseline Hemoglobin

Baseline hemoglobin will be an average of hemoglobin measurements within 28 days of Cycle 1 Day 1, excluding measurements within 7 days following RBC transfusion.

Baseline Transfusion Burden

Baseline transfusion burden will be calculated as the total amount of RBC transfusion during the 8 weeks prior to Cycle 1 day 1.

Baseline for Other Parameters

Baseline erythropoietin (EPO) is defined as the maximum test value within 28 days of Cycle 1 Day 1. For all other parameters, baseline is defined as the last observation on or prior to Cycle 1 Day 1.

End of Treatment (EOT)

Procedures and evaluations for the end of treatment visit should be performed on Day 113 (± 7 days) (28 days after the last dose of ACE-536).

Post Treatment Follow-Up (PTFU)

Procedures and evaluations for the post treatment follow-up visit should be performed on Day 141 (± 7 days) (28 days after EOT visit).

End of Study (EOS)

Procedures and evaluations for the end of study visit should be performed on Day 169 (± 7 days) (56 days after the Day 113/EOT visit).

Patients who discontinue treatment early should complete the end of treatment visit at the time of discontinuation and complete the post-treatment follow-up (PTFU) and EOS follow-up visits 28 days (± 7 days) and 56 days (± 7 days) after the EOT visit.

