5.7.2.6. Erythropoietin Parameters

Blood samples relating to erythropoietin parameters including serum erythropoietin levels, reticulocytes and nucleated RBCs will be taken at Screening, Day 1, 8, and 15 of Cycles 1, Day 1 of Cycle 2 and 4, EOT, PTFU and EOS visits. Descriptive statistics of observed values, absolute and percentage change from baseline values at each post baseline visit will be presented by dose cohort. Plots of erythropoietin parameters for both mean observed values and mean percentage change from baseline over time will be presented by dose cohort.

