5.7.3.3. Subgroup Analyses

Subgroup analyses of the efficacy endpoints will be performed for the following baseline parameters:

- RS mutation status (yes or no),
- Low (< 0.75 mg/kg) vs High (≥ 0.75 mg/kg) Dose Group
- SF3B1 mutation status (yes or no)
- Any splicing factor (yes or no)
- Baseline bone marrow blasts ($< 5\%$ or $\geq 5\%$)
- Baseline erythropoietin (EPO) (≤ 200 or > 200): (≤ 500 or > 500)
- IPSS risk group (low, Int-1, Int-2, or high)
- IPSS-R risk group (low, intermediate, high, very high)

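### Baseline EPO is the larger of two pre-dose values, so the reported change from baseline shows a fall in EPO even with no drug effect

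*SAP*

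**What the plan says.** SAP 5.1 (Definitions) gives EPO its own baseline: "Baseline erythropoietin (EPO) is defined as the maximum test value within 28 days of Cycle 1 Day 1". Hemoglobin and transfusion burden also have their own rules. For the rest, "For all other parameters, baseline is defined as the last observation on or prior to Cycle 1 Day 1". The SAP gives no reason for using the maximum, and the protocol does not define baseline EPO.

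SAP 5.7.2.6 says EPO samples are "taken at Screening, Day 1, 8, and 15 of Cycles 1, Day 1 of Cycle 2 and 4, EOT, PTFU and EOS visits". The schedules of events in both documents agree and require Cycle 1 Day 1 procedures before dosing, so a patient normally has two pre-dose EPO values.

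The baseline is used in these places:
- **Change from baseline (SAP 5.7.2.6):** "Descriptive statistics of observed values, absolute and percentage change from baseline values at each post baseline visit will be presented by dose cohort". Mean percentage change is also plotted.
- **Efficacy subgroups (SAP 5.7.3.3):** "Baseline erythropoietin (EPO) (≤ 200 or > 200): (≤ 500 or > 500".
- **Baseline table (SAP 5.4)** and, optionally, strata in the exposure-response analysis (SAP 5.10).

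Entry to cohort 2A (200 U/L or less) and cohort 3 (500 U/L or less) is judged on EPO at screening (SAP 3.1). For cohort 3, the SAP calls that screening value the baseline EPO.

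**The concern.** A maximum of two measurements is systematically higher than a single measurement of the same quantity. When every later visit contributes one value, the comparison tilts downward at every visit, whatever the drug does. EPO is named in the secondary pharmacodynamic objective (SAP 2), and the study has no untreated group, so a reader of the change tables and plots could not separate this artefact from a pharmacodynamic effect. Reticulocytes and nucleated RBCs, reported in the same section, follow the last-observation rule, so one section would mix two kinds of baseline.

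The second issue is classification. Cohort entry uses the screening value and the subgroups use the maximum, so the same patient can be at or below 200 U/L for entry and above 200 U/L for the subgroup.

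**Working it through.** The plan states no figure on this point, so there is none to reproduce.

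**Inputs.** From the documents: two pre-dose values (Screening and Cycle 1 Day 1), and one value at each later visit. Assumed, because the documents give nothing: no true change in EPO, and independent log-normal within-patient variation with log-SD *s* from 0.2 to 0.4.

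**1. Geometric-mean change.** The expected maximum of two standard normal values is 1/√π = 0.564, so the change is exp(-0.564·s) - 1.
- s = 0.2: exp(-0.113) - 1 = -10.7%
- s = 0.4: exp(-0.226) - 1 = -20.2%

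**2. Arithmetic mean percentage change** (the quantity plotted). The mean of a later value divided by the maximum is 2·exp(s²)·Φ(-s/√2), and 1 is subtracted.
- s = 0.2: 2 × 1.0408 × 0.4438 - 1 = -7.6%
- s = 0.4: 2 × 1.1735 × 0.3887 - 1 = -8.8%

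This is smaller than the geometric figure because the ratio is skewed to the right.

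**3. Mean absolute change.** The mean of the maximum is 2·Φ(s/√2) times the true mean.
- s = 0.2: 2 × 0.5562 = 1.112, a fall of about 11% of the true mean
- s = 0.4: 2 × 0.6114 = 1.223, a fall of about 22%

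**4. Share of patients showing a rise.** A later value exceeds the baseline only if it is the largest of three exchangeable values: probability 1/3, against 1/2 with a single-value baseline.

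**5. Simulation check** (1,000,000 patients, maximum of two, no true change):

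| Within-patient CV | Geometric-mean change | Mean percentage change | Patients with a rise |
|---|---|---|---|
| 10% | -5.5% | -4.7% | 33% |
| 20% | -10.6% | -7.6% | 33% |
| 30% | -15.3% | -8.9% | 33% |
| 50% | -23.3% | -7.6% | 33% |

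**6. Same check with the last pre-dose value.** The median and geometric-mean changes are 0% and half the patients show a rise. The mean absolute change is also 0, since both values have the same mean. The arithmetic mean percentage change is not 0: it is exp(s²) - 1, or +4.1% at s = 0.2 and +17.4% at s = 0.4. That is ordinary ratio skew, which affects any parameter summarised by mean percentage change from a single baseline value.

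**7. Relabelling in cohort 2A.** Given a screening value *v*, and treating the log difference between the two pre-dose values as normal with mean 0 and SD √2·s, the chance that Cycle 1 Day 1 exceeds 200 U/L is 1 - Φ(ln(200/v)/(√2·s)). Over CV 10% to 50% this is 0% to 15% at v = 100, 2% to 33% at v = 150, and 36% to 47% at v = 190. For a group of 25, with screening values drawn from assumed populations (median 40, 60 or 100 U/L; between-patient log-SD 0.8 or 1.0) and kept if 200 or less, the expected number relabelled is 0.1 to 2.8.

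**The case against.** **The consequences are small.** All summaries are descriptive with no hypothesis test (SAP 5.2), EPO change is one secondary pharmacodynamic parameter, and the EPO subgroups are listed under exploratory endpoints. The definition of mHI-E does not use EPO. Observed EPO values are also tabulated and plotted, and these do not depend on the baseline rule. If within-patient variation is similar across dose cohorts, the artefact is similar too, so contrasts between cohorts remain readable. All of this stands and limits the weight of the point. It does not make the reported change from baseline correct.

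**The size is assumed.** It rests on a within-patient variation and an independence that the documents do not supply. The geometric-mean figure also overstates the plotted mean percentage change. That is fair, and both figures are given for this reason. The direction needs only that the two pre-dose values vary.

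**A reader might infer that on-drug values enter the baseline**, because the 28-day window is not expressly limited to the days before dosing, and Days 8, 15 and 22 fall within 28 days after it. The documents do not support this. SAP 5.7.2.6 reports change at post-baseline visits, and its schedule includes those three days; they cannot also be baseline. SAP 5.1 words the baseline hemoglobin window in the same way. The IWG appendix likewise omits *prior* when it describes the 8-week transfusion window that SAP 5.1 defines as preceding Cycle 1 Day 1. A clarifying word is enough.

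**The choice of subgroup variable is partly a preference.** A single screening value is just as noisy, and a 200 U/L cut-point has no counterpart in the entry criteria of cohort 2B, expansion cohort 1 or the escalation cohorts. This stands. The maximum may be kept for grouping if it is labelled as such.

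**Conclusion.** The point holds for change from baseline. With no true effect and log-SD 0.2 to 0.4, the rule yields a mean percentage change of about -8% to -9%, a geometric-mean change of about -11% to -20%, and a rise in about a third of patients instead of half. These sizes depend on the assumed independent log-normal variation; the downward direction does not depend on the particular SD.

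For the subgroups the claim is weaker. The maximum can place some cohort 2A patients above 200 U/L, and in the same way some cohort 3 patients above 500 U/L. It need not move any. A reader might take this as a breach of the cohorts' entry limits. It is not, because entry is decided on the screening value and cohort results are summarised by cohort regardless of EPO subgroup. Nor does the rule necessarily affect the exposure-response analysis, since SAP 5.10 makes EPO strata optional. The overall mHI-E estimate is untouched.

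**What to change.** - **Change from baseline:** in SAP 5.1, define baseline EPO for SAP 5.7.2.6 as the last pre-dose value on or prior to Cycle 1 Day 1, which is the rule already used for most other parameters.
- **Window:** if a 28-day window is kept anywhere for EPO, add *prior to* so that it plainly means before dosing.
- **Subgroups:** if the maximum is kept for the 200 and 500 U/L groupings, name it as a separate classification variable and note that it can differ from the screening value used for cohort entry.
- **Reading the results:** because mean percentage change carries ratio skew under any single-value baseline, refer to the median, which SAP 5.2 already provides, when describing percentage change in EPO.

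The cost is a few words in the SAP and one changed derivation. No new data are needed.
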